5.8 Stopping Guidelines

At the end of stage I, lack of efficacy stopping guidelines will be implemented separately for each arm. If the Bayesian posterior probability of efficacy for a particular arm is $< 20\%$, it will be recommended that the arm be closed to further accrual. For lack of efficacy, an arm will be closed if the posterior probability is $\leq 20\%$ that the CR rate at Day 28 is greater than 35%. This is equivalent to stopping for lack of efficacy if 4 or fewer of the first 20 patients are CRs. Once the stopping criteria have been met for a particular arm, no more patients will be randomized to that arm.

After 20 patients have been accrued, this stopping rule for lack of efficacy results in the following stopping probabilities as a function of the true CR rate.

Table 5.8
STOPPING GUIDELINES

N Evaluable	Stop if # of CRs are	Probability of Stopping for Lack of Efficacy			
		CR=15%	CR=25%	CR=35%	CR=45%
20	≤ 4	83%	42%	12%	2%

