5 STATISTICAL CONSIDERATIONS

5.1 Study Design Synopsis

This study is a multi-center, randomized two-stage Phase II trial designed to evaluate several frontline treatments for acute GVHD. After 20 patients per treatment are evaluable (stage I), a stopping rule for lack of efficacy will be applied, so that future patients may be randomized to the most promising treatments. The remaining patients will be randomized in stage II to the treatments passing through stage I, to a maximum of 65 patients per arm or 180 patients total.

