5.3 Randomization

Randomization will occur separately in two strata. Stratum 1 consists of patients who had received MMF previously as GVHD prophylaxis and are not eligible to receive MMF again as GVHD treatment, while stratum 2 consists of patients who did not receive MMF previously as GVHD prophylaxis. Patients in stratum 1 will be randomized in equal proportions to the other three treatment arms. Patients in stratum 2 will be randomized in unequal proportions to all four arms (initially 40% to MMF and 20% to each of the other three arms). This unequal allocation was chosen to target approximately equal sample sizes per arm (45) by the end of the study, assuming 33% of patients will belong to stratum 1. Randomization in each stratum will occur using two sets of permuted blocks of varying sizes. One set of permuted blocks will determine MMF vs. not MMF for patients in stratum 2, while the other set will determine which of the other three arms the patient is assigned to. After 80 patients have been enrolled and followed up for the primary endpoint, two things will be assessed. First a stopping rule will be applied as described below to determine whether any of the arms should be closed for lack of efficacy. Second, the proportion of patients entering stratum 1 will be assessed. If the MMF treatment arm is closed for lack of efficacy, then we will revert to equal randomization for any remaining treatment arms. Otherwise, based on the number of non-MMF arms remaining (i.e. not closed for lack of efficacy) and the proportion of patients entering stratum 1, we will adjust the allocation probability P to MMF treatment in stratum 2 according to the following formula:

$$P = (k * i + 3 * (180 - i) - 4 * k * y) / (3 * (k + 1) * (180 - i) * (1 - r)),$$

where r=observed percent of MMF prophylaxis use so far, i=80 is the number accrued, k is the number of non-MMF treatment arms remaining, and y is the number assigned to MMF treatment. This formula is obtained by setting the expected final number of patients assuming allocation of P in stratum 2 to MMF treatment equal to the expected final number of patients in

each of the other treatment arms. Some examples of the new allocation rates are given in the table below, as a function of the observed MMF prophylaxis rate and the number of remaining arms. Also given are the expected sample sizes after 80 patients and after 180 patients in both the MMF arm and a representative non-MMF arm.

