5.5 Primary Hypothesis

Each arm will be compared to the historical rate of 35% CR at Day 28 of therapy. This will be done by computing a “Bayesian posterior probability of efficacy,” i.e., the Bayesian posterior probability that the response rate is > 35%, using a Beta (3.5, 6.5) prior distribution. This prior has a mean of 35% and a “weight” of 10 patients. If this posterior probability of efficacy is > 90%, the treatment is considered a candidate for further investigation based on the primary endpoint. No statistical comparisons between the arms will be performed: the purpose of the trial is only to identify treatments for further investigation through comparisons to a historical control of corticosteroids alone and is underpowered for comparisons among the arms.

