5.6 Study Design

Stage I: Randomize patients in two strata as described above until 80 patients are evaluable for the primary endpoint. After 80 patients are evaluable, apply the following stopping rule for lack of efficacy: if the Bayesian posterior probability of efficacy for a particular arm is < 20%, close the arm to further accrual. This Bayesian stopping rule is equivalent to stopping if the number of patients alive in CR at Day 28 is less than or equal to 4 out of 20.

Stage II: Continue randomizing patients after modifying the randomization scheme as described above. If the MMF treatment arm is dropped for lack of efficacy, then the randomization will be done equally among all remaining treatment arms. If not, then the randomization probabilities will be recomputed according to the rate of MMF prophylaxis use in the first 80 patients as well as the number of remaining non-MMF treatment arms that passed successfully through stage I. This randomization will be done up until a maximum of 65 per group or 180 patients have been accrued. At the end of the study, a treatment identifying a good candidate will be based on the primary endpoint if the Bayesian posterior probability of efficacy is $> 90\%$.

This Bayesian rule corresponds to a cutoff in terms of numbers of patients alive in CR at Day 28, which depends on the final enrolled sample size and therefore the number of treatment arms passing through stage I. Sample cutoffs are given in Table 5.6 below.

Table 5.6
CUTOFFS FOR PATIENTS ALIVE IN CR AT DAY 28

Number of Treatments Passing through Stage I	Final n per Treatment Group	Declare Treatment a Good Candidate if # of CRs is $\geq x$
1	65	29
2	65	29
3	52	24
4	45	21

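### The Stage I futility look is taken at 80 patients in total, but its count rule and Table 5.8 assume 20 per arm; at the plan's own expected arm sizes the posterior rule has other cutoffs, and an arm at 35% CR is closed with probability 13% to 20%, not 12%

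*Combined protocol and SAP*

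**What the plan says.** The plan gives two descriptions of when the Stage I look happens.

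- **Per arm.** Section 5.1: "After 20 patients per treatment are evaluable (stage I), a stopping rule for lack of efficacy will be applied". Section 5.8 also works with 20 patients in the arm, and Table 5.8 has a single row, for 20 evaluable patients.
- **In total.** Section 5.6: "Randomize patients in two strata as described above until 80 patients are evaluable for the primary endpoint". Section 5.3: "After 80 patients have been enrolled and followed up for the primary endpoint, two things will be assessed". The synopsis (Accrual Objective) and section 2.1 also refer to 80 evaluable patients.

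The rule itself is Bayesian. Section 5.6: "if the Bayesian posterior probability of efficacy for a particular arm is < 20%, close the arm to further accrual". The prior is given in section 5.5 ("using a Beta (3.5, 6.5) prior distribution"), with 35% as the reference rate. Section 5.6 equates the rule with 4 or fewer CRs out of 20, and section 5.8 repeats this: "This is equivalent to stopping for lack of efficacy if 4 or fewer of the first 20 patients are CRs". Table 5.8 then gives closing probabilities of 83%, 42%, 12% and 2% at true CR rates of 15%, 25%, 35% and 45%.

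Arm sizes at 80 patients are not fixed at 20. Stratum 2 is allocated "initially 40% to MMF and 20% to each of the other three arms", and stratum 1 cannot receive MMF. The table in section 5.3 expects, for MMF and for each other arm, 26 and 18 (MMF prophylaxis rate r = 0.20), 21 and 20 (r = 0.33, the planning case), 18 and 21 (r = 0.45), and 16 and 21 (r = 0.50).

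The threshold also varies. The synopsis closes an arm when the probability of a true CR rate below 35% exceeds 85%, which is a posterior of efficacy below 15%. Section 5.8 writes the 20% limit once as strictly less than and once as less than or equal to.

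**The concern.** A look at 80 patients in total and a look at 20 per arm coincide only if every arm happens to hold 20. The plan's own table does not expect that, even in the planning case. Away from 20, a fixed posterior threshold has a different count cutoff, so the count rule and the posterior rule can give opposite decisions on the same data. Where an arm has 16 or 18 patients at the look, a rule on its first 20 cannot be applied at all, and no other cutoff is printed.

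Closure ends randomization to the arm. Those who advise on it should have one rule with one answer, and closing probabilities that describe the look actually taken.

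**Working it through.** **Inputs.** Prior Beta(3.5, 6.5) and reference rate 35% (section 5.5); close if the posterior of efficacy is below 20% (sections 5.6 and 5.8); expected arm sizes at 80 patients (table in section 5.3); stated closing probabilities (Table 5.8).

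**Formulas.** With x CRs in n patients the posterior is Beta(3.5 + x, 6.5 + n − x). The cutoff c(n) is the largest x for which P(rate > 0.35) is below 0.20. The closing probability at true rate p is the binomial P(X ≤ c(n)).

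**Plan's figures reproduced.** At n = 20 the posterior of efficacy is 10.8% for 4 CRs and 20.3% for 5, so the cutoff is 4. The closing probabilities are 83.0%, 41.5%, 11.8% and 1.9%, matching Table 5.8. The expected sizes also reproduce: MMF = 80 × (1 − r) × 0.4 and each other arm = (80 − MMF)/3. At r = 0.33 this is 21.4 and 19.5, printed as 21 and 20.

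**Same rule at the expected sizes.**

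| n | Expected for | Cutoff | Posterior at cutoff / one more CR | P(close), CR 25% | CR 35% | CR 45% | CR 50% |
|---|---|---|---|---|---|---|---|
| 16 | MMF, r = 0.50 | ≤ 3 | 12.3% / 23.5% | 40.5% | 13.4% | 2.8% | 1.1% |
| 18 | MMF, r = 0.45; others, r = 0.20 | ≤ 4 | 16.2% / 28.4% | 51.9% | 18.9% | 4.1% | 1.5% |
| 20 | others, r = 0.33 | ≤ 4 | 10.8% / 20.3% | 41.5% | 11.8% | 1.9% | 0.6% |
| 21 | MMF, r = 0.33; others, r = 0.45 and 0.50 | ≤ 5 | 17.0% / 28.8% | 56.7% | 20.1% | 3.9% | 1.3% |
| 26 | MMF, r = 0.20 | ≤ 6 | 12.3% / 21.5% | 51.5% | 14.2% | 1.8% | 0.5% |

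No posterior here equals 20%, so the choice between < and ≤ changes no cutoff at these sizes.

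**Averaging over arm size.** Stratum sizes were drawn at random at each of the four values of r, with allocation within strata either held near its target, as blocks would do, or left fully random (20,000 draws each). The average closing probability at 35% CR is about 14% to 18%, depending on r, arm and allocation.

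**Where the two rules part.** At n = 21 the posterior rule closes whenever the first-20 rule does, and also when there are 5 CRs in the first 20 and the 21st patient is not a CR. At 35% CR that extra event has probability 20.1% − 11.8% = 8.3%. If 4 or fewer were instead applied to all patients in the arm, the closing probability at 35% CR would be 28.9% at n = 16, 9.2% at n = 21 and 2.4% at n = 26.

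**Synopsis threshold (posterior of efficacy below 15%).** The cutoffs at n = 16, 18, 20, 21 and 26 become 3, 3, 4, 4 and 6. The closing probabilities at 35% CR are 13.4%, 7.8%, 11.8%, 9.2% and 14.2%.

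**Final decision.** Take a final n of 45, declare at 21 or more CRs (Table 5.6), and ignore mortality stopping. The chance of declaring an arm a good candidate is then 7.0% to 7.1% at 35% CR and 72.3% to 72.4% at 50% CR, for an interim n of 16, 18, 20, 21 or 26.

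**The case against.** The plan has a fair defence. Every figure in Table 5.8 is right at the size it is labelled with. The rule can be computed at any n from the stated prior, and a count cutoff that steps with n is a feature of any posterior threshold on discrete data. The cutoff of 4 is also the posterior cutoff at 17, 18 and 19. In the planning case three of the four arms are expected at about 20, so 20.1% applies to the expected MMF size only. Finally, 35% is the rate at which an arm counts as ineffective, so closing such an arm more often is not in itself a harm. All of this stands. It limits the size of the point, but it leaves two conflicting rules and no cutoff for arms that do not hold 20.

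Three stronger readings are tempting and are not supported.

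- A reader might infer that Table 5.8 is miscalculated. It is not; the defect is that it describes one size only.
- A reader might infer that the printed values are the most favourable throughout. That is true at these sizes only in the 35% column: n = 16 gives lower closure at 15% (79.0% against 83.0%) and at 25% (40.5% against 41.5%), and n = 26 is slightly lower at 45%.
- A reader might infer that power is overstated. Closure at 50% CR is only 0.5% to 1.5%, and the single-arm declaration probabilities barely move.

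**Conclusion.** The futility rule is internally inconsistent. The stated equivalence to 4 of 20, and the 12% closing probability at 35% CR, do not describe a look taken at 80 patients in total. Under the 20% threshold the closing probability at 35% CR is 13.4% to 20.1% at the expected sizes other than 20, and about 14% to 18% on average. At 45% CR it is 1.8% to 4.1%, against 2% stated. An arm with 5 CRs in 21 can be closed under one written rule and kept open under the other.

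The conclusion assumes the section 5.5 prior, the expected sizes in section 5.3, and all evaluable patients in the arm being counted. The size and direction of the discrepancy depend on the threshold: under the synopsis figure, 5 of 21 stays open and closure at 35% CR is 7.8% to 14.2% at the five sizes. The contradiction over when to look, and over which patients count, remains under either threshold. The consequence is an ambiguous early-closure decision and an incomplete table, with negligible effect on the final declaration.

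**What to change.** Keep the look at 80 evaluable patients in total, because the reallocation formula in section 5.3 is written for i = 80 and needs k, the number of non-MMF arms remaining, at that same moment. Then:

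1. Align section 5.1 with sections 5.3 and 5.6.
2. State that the posterior rule, applied to all evaluable patients in the arm at that look, governs. Remove the claim of equivalence and the reference to the first 20 patients from section 5.8, and the matching sentence from section 5.6.
3. Reconcile the 20% threshold with the 85% statement in the synopsis, and write the inequality one way.
4. Replace Table 5.8 with cutoffs and closing probabilities for arm sizes of about 14 to 28. If 20% is kept, the cutoffs are ≤ 3 for 14–16, ≤ 4 for 17–20, ≤ 5 for 21–23, ≤ 6 for 24–26 and ≤ 7 for 27–28.

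The cost is wording and one table. If 20% is kept, the table will show a somewhat higher closing probability at 35% CR than the present 12%. Moving to a per-arm trigger at 20 would make Table 5.8 hold as printed, but it is a design change: arms would reach 20 at different times and k might not be known when the allocation is recomputed.

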5.8.1 Stopping Guidelines for Mortality

Mortality of 25% at Day 28 of therapy would be considered unexpected and an unacceptable number of excess deaths compared to the anticipated and historical rate of approximately 10%.

Therefore, a stopping rule for Day 28 mortality will be applied after every 10 patients are accrued per group. A particular arm will close at interim look t if the number of deaths on that arm is $\geq x_t$, e.g., if four or more deaths in the first 10 patients or six or more deaths in the first 20 patients, etc. as detailed in Table 5.8.1 below. Looking after every 10 patients per group corresponds approximately to looking at mortality every 2 months starting with the third month (i.e. after months 3, 5, 7, 9), assuming an accrual rate of 20 patients/month. If one or more arms should close after stage I, we will review the mortality data slightly more frequently.

The stopping rules and probabilities of stopping at each interim look are given in the table below. Note that the final sample size per arm is variable due to the stopping rule for lack of efficacy; therefore, the cumulative stopping probabilities are also given for cumulative sample sizes of 40 and 60. In summary, a treatment with a 10% mortality rate, which is what is expected based on historical data, will have a 2.6% chance of triggering the stopping rule for mortality. If that mortality rate for a treatment under investigation should increase to 25%, a 15% increase in mortality over the historical rate, we will have a 65.2% chance of triggering the stopping rule within 40 patients and a 76.8% chance of triggering the stopping rule within 65 patients.

Table 5.8.1
STOPPING PROBABILITIES FOR VARIOUS MORTALITY RATES AT DAY 28
(Stopping rule is defined as stop if the number of deaths at look t is $\geq x_t$)

Look (t)	Total N	x_t	Probabilities of Stopping at Look t for True Mortality Rates of				
			p = 0.1	0.15	0.2	0.25	0.3
1	10	4	1.4%	5.3%	12.7%	22.8%	35.2%
2	20	6	0.7%	4.2%	11.1%	20.4%	26.4%
3	30	8	0.3%	2.7%	7.5%	13.2%	15.0%
4	40	10	0.2%	1.8%	5.8%	8.8%	9.0%
5	50	12	0.0%	1.6%	4.7%	6.5%	5.4%
6	60	14	0.0%	1.0%	3.8%	5.1%	3.2%
Cumulative probability of stopping after 40 patients			2.6%	14.0%	37.1%	65.2%	85.6%
Cumulative probability of stopping after 60 patients			2.6%	16.6%	45.6%	76.8%	94.2%

If lack of efficacy or mortality rates significantly exceed pre-set thresholds, the NHLBI will be notified in order that the DSMB can be advised. Policies and composition of the DSMB are described in the BMT CTN's Manual of Procedures.

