4.2 Study Monitoring

4.2.1 Follow-up Schedule

The Follow-up Schedule for scheduled study visits is outlined in Table 4.2.1. A detailed description of each of the forms and the procedures required for forms completion and submission can be found in the Data Management Handbook and User's Guide.

Follow-up Assessments: The timing of follow-up visits is based on the date of randomization. Following randomization, the Transplant Center can print a Patient Visit Schedule listing target

dates for assessments. Weeks 1-8 visits are primarily for acute GVHD scoring. The subsequent visits are for follow-up reports.

Criteria for Forms Submission: Criteria for timeliness of submission for all study forms are detailed in the Data Management Handbook and User's Guide. Forms that are not received at the DCC within the specified time will be considered delinquent. Transplant Centers can view past due forms via the Web-based data entry system. A missing form will continue to appear until the form is entered into the DCC's master database, or until an exception is granted and entered into the Missing Form Exception File, as detailed in the Data Management Handbook and User's Guide.

Reporting Patient Deaths: The Recipient Death Information must be entered into the web-based data entry system within 24 hours of knowledge of a patient's death. If the cause of death is unknown at that time, it need not be recorded at that time. However, once the cause of death is determined, the form must be updated.

CIBMTR Data Reporting: All transplant centers participating in BMT CTN protocols are required to register all of their transplant patients, not just those enrolled on BMT CTN protocols, with the CIBMTR, using standard CIBMTR Preregistration and Transplant Essential Data Forms (instructions available at www.ibmtr.org). CIBMTR Day 100 Report Forms (including the Core, Graft and Disease Inserts) and CIBMTR Follow-up Forms (including the Core and Disease Inserts) are required for patients enrolled on BMT CTN protocols and will be submitted directly to the CIBMTR at the times specified in the Data Management Handbook and User's Guide.

Table 4.2.1
FOLLOW-UP SCHEDULE

Assessment Time	Target Day¹ (Days Post-Enrollment)
1 week	7 days
2 weeks	14 days
3 weeks	21 days
4 weeks	28 days
5 weeks	35 days
6 weeks	42 days
7 weeks	49 days
8 weeks	56 days
90 days	90 days
120 days	120 days
6 months	180 days
9 months	270 days

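### Section 5.8.1 closes an arm for Day 28 mortality only at 10-patient looks and does not say what happens to randomization when the deciding death is reported between looks

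*Combined protocol and SAP*

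**What the plan says.** Section 5.8.1 sets the timing of the mortality rule: "a stopping rule for Day 28 mortality will be applied after every 10 patients are accrued per group". Closure is tied to the look: "A particular arm will close at interim look t if the number of deaths on that arm is" at or above x_t. The worked example is "if four or more deaths in the first 10 patients or six or more deaths in the first 20 patients", and Table 5.8.1 gives the boundaries as 4/10, 6/20, 8/30, 10/40, 12/50 and 14/60. On the calendar, the schedule "corresponds approximately to looking at mortality every 2 months starting with the third month (i.e. after months 3, 5, 7, 9", at 20 patients per month overall. Somewhat more frequent review is promised if arms close after stage I, but that still means discrete looks. No pause in accrual is mentioned.

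Three other places bear on the point:

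- **Section 5.8**, at the end of the lack-of-efficacy paragraph: "Once the stopping criteria have been met for a particular arm, no more patients will be randomized to that arm".
- **End of Section 5.8.1**, on mortality or lack of efficacy beyond the thresholds: "the NHLBI will be notified in order that the DSMB can be advised". It then says "Policies and composition of the DSMB are described in" the network's Manual of Procedures, which is not among the documents.
- **Section 4.2.1**, on death information: it "must be entered into the web-based data entry system within 24 hours of knowledge" of the death. Section 4.2.4 also sets a 24-hour limit for reporting deaths.

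**The concern.** The count of Day 28 deaths among the first 10t patients can only rise. When it reaches x_t, the result of look t is settled, provided accrual reaches patient 10t and the arm has not already closed for another reason. Nothing learned later can reverse it. Yet Section 5.8.1 places closure at the look and does not say that randomization stops sooner. Followed literally, it lets patients be randomized to an arm that has already met the protocol's own threshold for excess deaths, even though the death is in the database within a day of being known.

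The issue is limited to patients randomized after the deciding death is reported. The 28 days of follow-up that the endpoint needs are not in question.

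**Working it through.** **1. Look timing.** With four arms, 20 patients per month is 20/4 = 5 per arm per month. Look t therefore needs 10t/5 = 2t months of accrual plus 28 days of follow-up, or about months 3, 5, 7 and 9, as the plan states. The planned total of 180 gives 180/(4 × 9) = 5 per arm per month over the nine months in Section 5.2, and 180/(4 × 12) = 3.75 over the twelve months in the synopsis. Both rates are used below.

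**2. Reproducing Table 5.8.1.** Let q_t(k) be the probability of reaching look t without an earlier stop and with k deaths. Then q_t(k) = Σ_j q_{t−1}(k−j) · C(10,j) p^j (1−p)^{10−j}, where the sum keeps only earlier counts below x_{t−1}. The stopping probability at look t is the sum of q_t(k) over k ≥ x_t.

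At p = 0.25 the six looks give 22.41%, 19.76%, 13.40%, 9.36%, 6.81% and 5.12%. By 40 patients: 22.41 + 19.76 + 13.40 + 9.36 = 64.93%. Adding 6.81 + 5.12 gives 76.86% by 60.

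| True mortality | By 40: exact (plan) | By 60: exact (plan) |
|---|---|---|
| 10% | 2.5% (2.6%) | 2.6% (2.6%) |
| 15% | 13.7% (14.0%) | 16.0% (16.6%) |
| 20% | 37.3% (37.1%) | 45.8% (45.6%) |
| 25% | 64.9% (65.2%) | 76.9% (76.8%) |
| 30% | 85.3% (85.6%) | 93.7% (94.2%) |

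All differences are below 0.7 percentage point, so the plan's table holds.

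**3. Closing at the deciding death does not change these probabilities.** If the x_t-th death among the first 10t patients has occurred before look t, the count at look t is at least x_t. If the count at look t is at least x_t, that death occurred at or before the look. The two rules close the same arms, and only the date differs.

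**4. How often the boundary is reached early.** Taking patients in enrolment order, with deaths known at once, 77% of stopping paths at p = 0.25 cross the boundary before the 10t-th patient, by 2.2 patients on average over all stopping paths. This ignores follow-up time, which step 5 adds.

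**5. Patients and days saved.** Assumptions not in the documents: Poisson accrual, the distribution of death times within 28 days, and a 1-day lag from death to report. Each look is held when patient 10t completes 28 days, plus the lag. The cap is 45 per arm, the Section 5.3 target. There were 100,000 simulated arms per cell at p = 0.25. Paired figures are for 5 and 3.75 patients per arm per month.

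| Death timing | Fewer patients per closing arm | Days earlier | Fewer patients, mean over all arms | Closing arms saving nobody |
|---|---|---|---|---|
| Early, 28 × Beta(1,2) | 5.0 / 4.3 | 31 / 35 | 3.2 / 2.8 | 4% / 6% |
| Uniform | 4.2 / 3.7 | 26 / 31 | 2.7 / 2.4 | 10% / 12% |
| Late, 28 × Beta(2,1) | 3.5 / 3.2 | 22 / 26 | 2.3 / 2.1 | 15% / 17% |
| All on Day 28 | 2.1 / 2.1 | 13 / 17 | 1.4 / 1.4 | 41% / 41% |

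For example, with uniform deaths at 5 per month, closing arms enrol 26.2 patients under the look rule and 22.0 under the alternative: 26.2 − 22.0 = 4.2. Averaged over all arms this is 4.2 × 0.649 = 2.7. Both rules closed the same arms in every run, as step 3 requires.

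**6. Sensitivity.**

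- Cap of 65 per arm: 2.1 to 5.0 per closing arm, 1.6 to 3.9 over all arms.
- Five days from death to report (cap 45): 1.6 to 4.3 per closing arm, 1.1 to 2.8 over all arms.
- True mortality 30%: 2.3 to 5.2 per closing arm.
- True mortality 10%: 0.04 to 0.11 over all arms.

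**The case against.** The strongest reply is that the plan already covers this. The Section 5.8 sentence on ending randomization stands in the parent section and is not expressly limited to efficacy. The example of four deaths in the first 10 patients can be read as met the moment the fourth is known. That is a fair reading, but not a decisive one: the sentence ends the lack-of-efficacy paragraph, and Section 5.8.1 defines the mortality criterion at the look. The text supports two readings with different consequences for patients.

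Second, notification of the NHLBI is not tied to a look, and what follows is left to DSMB policy in a manual we have not seen. A between-look procedure may exist there. This stands, so only the silence of the protocol can be asserted. The DSMB's role also means that closure is certain arithmetically rather than operationally.

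Third, periodic looks are an ordinary design. The plan discloses their spacing, boundaries and stopping probabilities, and the figures reproduce. This stands too: nothing is miscalculated.

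Fourth, the gain is conditional and modest. It arises only in an arm with excess mortality that closes, and it depends on assumed death timing. The simulation also leaves out stage I closure for lack of efficacy. Including it, with an assumed CR rate of 25% to 35%, lowers the all-arm figure for uniform deaths at 5 per month from 2.7 to about 2.4 to 2.6. These points limit the weight of the concern but do not remove it.

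**Conclusion.** The concern holds as a low-cost improvement. No passage expressly closes or suspends an arm when the deciding death is reported between looks, and Section 5.8.1 taken literally allows randomization to continue. The average cost at 25% mortality is 2.1 to 5.0 patients per closing arm with a 1-day reporting lag, and 1.6 to 4.3 with a 5-day lag (cap 45). Death timing, Poisson accrual and reporting lag are assumptions; the accrual rates and caps follow the plan. Confidence is medium, because the Section 5.8 sentence or the Manual of Procedures may already be meant to deal with this.

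**What to change.** Add one sentence to Section 5.8.1: randomization to an arm is closed, or suspended pending DSMB advice, as soon as the x_t-th Day 28 death among the first 10t patients on that arm has been reported and verified, with the Table 5.8.1 boundaries unchanged. If the Section 5.8 sentence or the Manual of Procedures already provides for this, say so in 5.8.1.

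The cost is operational: a running death count per arm, prompt verification that each reported death is a Day 28 death among the relevant patients, and possibly unscheduled contact with the DSMB. Boundaries, stopping probabilities and planned sample size do not change.
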